5.1 INCLUSION CRITERIA

Aim 1	HCW	18 years or older
	Policymakers	18 years or older Employed currently or in past at national/county or partner level
	Other stakeholders	18 years or older Relevant experience with adolescents
All aims	Clinics	Approximately 150 adolescents in care Active EMR system Willing to participate in the study
	HCW	18 years or older Working with ALHIV in participating clinics Provision of informed consent Willing and able to give informed consent
Aim 1	Stakeholders in adolescent care	18 years or older Working in adolescent health Provision of informed consent Willing and able to give informed consent
Aim 2	Adolescents	Ages 10-24 years HIV-positive Enrolled in HIV care Provision of informed consent (intervention/surveys and FGDs/IDIs) Willing and able to give informed consent (intervention/surveys and FGDs or IDIs) AYA15-17 years that are considered mature/emancipated minors will provide informed consent without caregiver consent; For 10-17 year old AYA, provision of caregiver informed consent
	Caregivers	18 years or older Caregiver of 10-17 years ALHIV Provision of informed consent Willing and able to give informed consent

5.2 EXCLUSION CRITERIA

All aims	Clinics	Participating in other studies that could overlap procedures/clients
	Adolescents, HCW, caregivers, adolescent	Not able or willing to give informed consent

Adapted from NIH Behavioral and Social Intervention Clinical Trial Protocol Template v3.0 - 20180827

	stakeholders	
--	--------------	--

5.3 LIFESTYLE CONSIDERATIONS

NA

5.4 SCREEN FAILURES

Screen failures are defined as clinics that are not included in the final list of clinics for randomization. After randomization, we do not anticipate to re-screen or include additional facilities.

5.5 STRATEGIES FOR RECRUITMENT AND RETENTION

Recruitment

Intervention adaptation workshop

Policy makers at national and county level, adolescent representatives, frontline HCW, adolescent caregivers and representatives from HIV care partners will be purposively selected by the study team to participate in an intervention development workshop. Recruitment will be consecutive until at least 40 participants are reached. A script outlining talking points, purpose and scope of work will be used for recruitment. Written informed consent for participation and audio-recording of sections of the proceedings will be obtained.

Intervention optimization (pilot)

Following adaptation of intervention materials, HCWs from 2 clinics will pilot the adapted intervention for up to 3 months using a modified quality improvement approach. The 2 HIV clinics will be purposively selected by the study team to participate in the pilot activities from a pool of HIV clinics involved in the formative phase of the study.

Cluster RCT

The sampling frame will consist of all 55 clinics in participating counties that were part of the earlier phase of the study or that have been identified as potential clinics. Among those, up to 24 clinics that meet eligibility criteria, have the highest AYA enrollment and whose leadership is willing to participate will be selected and randomized to intervention or control.

Adolescent and caregiver surveys

A proportion of ALHIV in participating facilities (~150 per site) and caregivers (~45 per site) will be enrolled to participate in surveys to determine ALHIV behavior, self-efficacy and co-factors of retention and viral suppression. Clinic staff members will refer ALHIV currently in HIV care to our trained study team for eligibility screening for the ALHIV longitudinal cohort. A standard recruitment script with talking points will be used. Recruitment will be conducted during different days and times of the week, during at least 2 school breaks and 'youth friendly days' to maximize enrollment. ALHIV who meet eligibility criteria will be invited to enroll in the cohort and complete

Adapted from NIH Behavioral and Social Intervention Clinical Trial Protocol Template v3.0 - 20180827

behavioral surveys at enrollment and every 6 months thereafter. Clinic staff members will refer to the study team a purposeful sample of caregivers of adolescents coming in for routine clinic visits. A large number of adolescents come to clinic alone; the study will only recruit caregivers who accompany adolescents. Caregivers who meet eligibility criteria will be invited to enroll and complete caregiver surveys at enrollment and at 12 months.

HCW surveys

HCW in participating sites working in the ALHIV clinic will be invited to participate in health service and implementation surveys. A script outlining talking points, purpose and scope of work will be used for recruitment. Written informed consent for participation will be collected from all participants prior to study activities.

Participant incentives

The study will provide reimbursement for transportation costs, accommodation and meals during the workshop and provide a per-diem allowance equal to current rates used by organizations or facilities where the HCWs work.

Adolescents and caregivers who participate in surveys will be reimbursed KSH 200 (\$2.00 USD). HCW attending study related meetings and completing surveys will be reimbursed KSH 1000 (~10USD).

Population justification

This study will be conducted in ALHIV age 10-24 years old, who have a high risk of mortality, and require innovative client-centered strategies to improve retention, adherence, and viral suppression. The study will be conducted in Kenya, where 140,000 adolescents (ages 10-19) have HIV, and HIV is among the leading causes of mortality in this age group.

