Description of Sites/Facilities Enrolling Participants:	Aim 1: 2 HIV clinics in Homa-bay, Migori or Kisumu. Aim 2: up to 24 HIV clinics in Homa-bay, Migori or Kisumu.
Description of Study Intervention/Experimental Manipulation:	Data-informed Stepped Care (DiSC) intervention is comprised of a system to assign ALHIV to different levels of care depending on their current and anticipated health care needs. The intervention will be delivered at the individual level by HCW providing routine care during routine HIV clinic visits.
Study Duration*:	24 months
Participant Duration:	24 months

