5 STUDY POPULATION

Aim 1

Intervention development: Policy makers at national, county and care partner levels, HCW, ALHIV and caregivers as well as other stakeholders in HIV care will be invited to participate in an intervention development workshop.

HCWs in 2 facilities participating in the completed formative phase of the study will pilot the intervention in their clinics.

Aim 2

Cluster RCT: We will conduct this study at up to 24 HIV care and treatment facilities located in Kisumu, Homa-Bay, Migori County.

The population of interest is ALHIV age 10-24 enrolled in participating clinics, caregivers of adolescents and young adults and HCW offering services. The intervention will be administered by existing HCW, who will also participate in implementation surveys, interviews, and focus groups to assess health service and implementation outcomes. A cohort of ALHIV ages 10-24 years will also be enrolled to participate in longitudinal surveys. A subset of ALHIV and caregivers of ALHIV will also complete satisfaction surveys at the end of the trial.

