HCWs and AYA in participating sites will consent to participate in the pilot phase which includes intervention administration, twice-monthly intervention adaptation meetings, as well as implementation surveys. At the start of the pilot, HCWs will complete a short demographic form to collect socio-demographic information. HCWs will be introduced to the adapted intervention materials, trained on how to use them, and encouraged to make small adaptations and changes to the way they implement the intervention throughout the pilot period. If a new HCW enters the facility during the pilot, they will also be trained on the intervention materials and have socio-demographic information collected. An implementation/adaptation log will be used to track changes in implementation and HCWs will participate in twice-monthly planning and feedback meetings. Meetings will be audio recorded and transcribed when necessary. Transcripts will not include HCW names. Routinely collected data at the facility, such as the number of adolescents attending and the number of adolescents exposed to the intervention, will be collected to monitor implementation outcomes of adoption and reach. Following the pilot period, HCWs from clinics who participated in the pilot will take part in individual in-depth interviews (IDIs) or focus group discussions (FGDs) to share their suggestions for optimizing the intervention based on their pilot experience. IDIs and FGDs will be audio recorded and will be transcribed verbatim. Transcripts and notes from twice-monthly meetings will be analyzed to identify themes related to how to revise intervention materials and implementation. After the pilot phase, the tool will be further refined with input from selected members who participated in the intervention development workshops prior to use in the RCT phase.

Adapted from NIH Behavioral and Social Intervention Clinical Trial Protocol Template v3.0 - 20180827

Cluster RCT

Intervention details, administration and assessments are described in the sections above (see section 6.1 and 6.2).

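### The two DiSC pilot clinics are not excluded from the cluster-trial sampling frame, so a clinic already trained in DiSC could be randomised to control

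*Protocol*

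**What the plan says.** **Pilot.** Protocol 5.5 says of the pilot: "The 2 HIV clinics will be purposively selected by the study team to participate in the pilot activities from a pool of HIV clinics". That pool is the set of formative-phase clinics. Section 5 agrees: "HCWs in 2 facilities participating in the completed formative phase of the study will pilot the intervention in their clinics". The pilot lasts up to 3 months (5.5). Section 8.1 describes the exposure: "HCWs will be introduced to the adapted intervention materials, trained on how to use them". Consenting adolescents receive the intervention, and staff attend adaptation meetings twice a month.

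**Trial.** The frame in 5.5 reads: "The sampling frame will consist of all 55 clinics in participating counties that were part of the earlier phase of the study". The sentence goes on to add clinics identified as potential sites. From this frame, "up to 24 clinics that meet eligibility criteria, have the highest AYA enrollment and whose leadership is willing to participate will be selected and randomized". The synopsis puts both stages in the same three counties: "Aim 1: 2 HIV clinics in Homa-bay, Migori or Kisumu. Aim 2: up to 24 HIV clinics in Homa-bay, Migori or Kisumu".

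**Eligibility.** Section 5.1 has one list of clinic inclusion criteria for all aims: about 150 adolescents in care, an active EMR and willingness. The only clinic exclusion in 5.2 is "Participating in other studies that could overlap procedures/clients".

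**Allocation and comparator.** Randomisation is 1:1 and restricted by county only (Protocol 4.1). Control clinics are to continue standard of care (Protocol 4.1; SAP 1.2), and their training covers data collection only (Protocol 6.1.2).

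**The concern.** The pilot clinics meet the description of the frame, and no rule in either document takes them out. The exclusion in 5.2 refers to other studies. The pilot is Aim 1 of this study, so the criterion does not clearly apply. Neither document fixes the arm of a pilot clinic, sets a washout, or plans an analysis without the pilot clinics.

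A control clinic whose staff have been trained in DiSC and have delivered it is not the comparator that the SAP objective describes. Any practice that persists would move control retention towards the intervention level and shrink the estimated effect. Receiving differentiated care, a secondary outcome in the SAP, is also exposed, because assigning adolescents to steps acts on it directly. With 12 clinics per arm, one clinic is 1/12, about 8%, of its arm.

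**Working it through.** **1. Can a pilot clinic reach the control arm?** Each step is open on the text.
- It is a formative-phase clinic in the three counties, so it is in the frame.
- It can meet the shared inclusion criteria, and the exclusion for other studies does not clearly catch it.
- It enters if its adolescent and young adult (AYA) enrolment ranks high enough and its leadership agrees. The documents give neither the identity nor the size of the pilot clinics, so this step is unknown.
- Once in, only county balance constrains its arm.

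**2. Chance of allocation to control, given selection** (24 clinics, 12 per arm, county restriction ignored).
- One pilot clinic selected: 12/24 = 50%.
- Both selected: P(both intervention) = (12 × 11)/(24 × 23) = 0.239. So P(at least one control) = 0.761, and P(both control) = 0.239 by symmetry.
- With the protocol's minimum of 20 clinics: 1 − (10 × 9)/(20 × 19) = 0.763.

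**3. The plan's own sample-size figures.**
- Protocol Table 3a reproduces with the standard unmatched cluster formula, c = 1 + (1.96 + 0.84)² × [p0(1−p0)/m + p1(1−p1)/m + CV²(p0² + p1²)]/(p1−p0)². For 75% vs 93%, m = 100 and CV 0.15 it gives 9.39, so 10 per arm as stated. The other cells also agree, apart from rounding in one (10.004, stated as 10).
- The SAP table reproduces to within one facility, in the retention cells checked, as an ICC design effect. For 75% vs 90%, m = 50 and ICC 0.10: n per arm = 7.849 × (0.75 × 0.25 + 0.90 × 0.10)/0.15² = 96.8. Multiplying by (1 + 49 × 0.10)/50 gives 11.4, so 12 as stated. The SAP text calls the 0.10 a coefficient of variation, but the table's figures follow from reading it as an ICC.

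**4. Dilution.** Let k be the number of pilot clinics in control and c the fraction of the effect that carries over. With 12 equal-sized clinics per arm, observed difference = 15 × (1 − kc/12).

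| k | c = 0.5 | c = 1 |
|---|---|---|
| 1 | 14.4 | 13.75 |
| 2 | 13.75 | 12.5 |

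**5. Power.** Control retention becomes 0.75 + (p1 − 0.75) × kc/(clinics per arm). The first row uses a two-proportion test on the effective sample size (12 × 50/5.9 = 101.7 per arm). The second uses the cluster formula in step 3.

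| Case | No carry-over | k = 1, c = 0.5 | k = 1, c = 1 | k = 2, c = 1 |
|---|---|---|---|---|
| SAP: 12 per arm, 75% vs 90%, m = 50, ICC 0.10 | 80.8% | 78.0% | 74.8% | 67.8% |
| Protocol: 10 per arm, 75% vs 93%, m = 100, CV 0.15 | 82.7% | 78.4% | 73.6% | 62.8% |

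The carry-over fractions are assumptions, because the documents give none.

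**The case against.** The best reply is that being in the frame is not being in the trial. Up to 24 of 55 clinics are chosen, mainly by enrolment, and the pilot clinics may rank too low or never be put forward. If selection were random, which it is not, both would be chosen with probability (24 × 23)/(55 × 54) = 19%, and at least one would end up a control with probability 1 − (43 × 42)/(55 × 54) = 39%. The stated intent that controls receive standard of care also suggests that nobody meant to use a pilot clinic as a control.

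Carry-over may also be modest. The pilot is short, and the tool is refined after it (8.1). Trial intervention clinics get fresh training and a supported start of about 3 to 6 months (6.2.1), which a control clinic would not get. With half carry-over from one clinic, the loss is 0.6 points and about 3 points of power in the SAP case.

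These arguments limit the size of the problem and stand as far as that goes. They do not supply the missing rule. The substitution provision in 4.1 gives no clear ground for removal, because a pilot clinic breaches no eligibility criterion, and 5.4 anticipates no re-screening after randomisation.

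**Conclusion.** The gap is real: read literally, the frame and exclusion rules allow a DiSC-trained clinic to be a control. Under the assumptions above (equal clinic sizes, half to full carry-over), a 15-point effect would be seen as 14.4 to 13.75 points with one such clinic and 13.75 to 12.5 with two. The bias is towards no effect.

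Four stronger readings are tempting, but the documents do not support them.
- A reader might infer that pilot clinics will be in the trial, or that 76% is the overall chance of a contaminated control. The 76% applies only if both are selected, and the probability of that is unknown.
- A reader might infer that a former pilot clinic keeps the tool and its step assignments. No passage says so, and full carry-over is an upper bound.
- A reader might infer that the 12 months of records before first abstraction form a baseline that overlaps the pilot. In Protocol 8.1 that window decides whose records are included. The SAP counts missed visits after enrolment, and the pilot's dates are not given.
- A reader might infer that a pilot clinic in the intervention arm inflates the effect through a head start. That is possible, but all intervention clinics receive adaptation support, and nothing in the documents sizes it.

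**What to change.** **Before randomisation.** Add participation in the Aim 1 DiSC pilot to the clinic exclusions in Protocol 5.2, and define the frame in 5.5 as the 55 clinics less the pilot clinics. If both are among the 55, 53 remain for up to 24 places and the sample size is unchanged. The cost is one line in each section, and up to two high-volume clinics may be replaced by the next largest.

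**If a pilot clinic has already been randomised.** Keep the intention-to-treat analysis as primary, report that clinic's arm in the CONSORT diagram, and add to SAP 3.4 a pre-specified sensitivity analysis of missed visits without the pilot clinics. The cost is one extra model.

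If no pilot clinic was selected, one sentence saying so closes the point.

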6 STUDY INTERVENTION(S) OR EXPERIMENTAL MANIPULATION(S)

6.1 STUDY INTERVENTION(S) OR EXPERIMENTAL MANIPULATION(S) ADMINISTRATION

6.1.1 STUDY INTERVENTION OR EXPERIMENTAL MANIPULATION DESCRIPTION

The Data-informed Stepped Care (DiSC) intervention is comprised of a system to assign ALHIV to different levels of care, or “steps”, depending on their current and anticipated health care needs. Stepped care is a model grounded in Stages of Change Theory and has been used in mental health fields to organize provision of services, and to support clients, HCWs, and caregivers to identify interventions tailored to individual need. HCWs at participating sites will assign ALHIV to different levels or intensity of HIV services. The trajectory of services moves from a relative position of ALHIV autonomy to more intensive service provision. Intervention steps could start with multi-month refills or community treatment delivery, then social support activities (support groups, life skills activities), progress to individualized services (text messaging, ‘big brother/sister’ older peer support, motivational interviewing), and ultimately a case management approach involving referrals to specialized care like mental health or gender-based violence services, individualized counseling, and active tracking of individual participation in support and care services. The stepped care framework is designed to be flexible, to accommodate variable

Adapted from NIH Behavioral and Social Intervention Clinical Trial Protocol Template v3.0 - 20180827

individual and social support services available at each facility. A sample of potential intervention steps is presented below:

Sample intervention steps

Levels	Criteria for eligibility	Regular care	Additional HCW provided	Additional clinic recommended
Stepped down care	Meets MoH criteria except age	-Differentiated care	None	-Support groups (optional)
Not retained	At risk for loss	-3 monthly visits	-Pre-clinic reminders (text) -Individual peer support -3 monthly adherence counseling	-Support group
Viral failure	At risk for viral failure OR VL under 1000 but detectable	-Monthly visits (6 weekly for school going)	-Monthly adherence counseling -Motivational interviewing (one round of several sessions) OR Coaching -Individualized ART pick-up strategies	-Support group -Caregiver or support person DOTS
Failed	Unsuppressed at last measure	-Monthly visits (6 weekly for school going)	-2 weekly adherence sessions (could make some on phone) -Accelerated repeat test timeline (3 month) -Prompt switch after second test -Case manager -DOTS by HCW (or caregiver/family)	-Support group -Special treatment failure support groups -Home visit by HCW -Viremia clinics

6.1.2 ADMINISTRATION AND/OR DOSING

The study team will conduct training for HCWs at intervention and control sites. At intervention sites, the training will focus on intervention use and data collection while in control sites, training will focus on data collection. At baseline, the study teams will assist HCWs to identify score categories for each step of care. The clinical tool will be uploaded onto handheld tablets or on paper tools, according to HCW preferences and will be used at ALHIV scheduled visits.

6.2 FIDELITY

6.2.1 INTERVENTIONIST TRAINING AND TRACKING

The intervention will be adapted and optimized prior to the RCT phase in an intervention development workshop and piloted in 2 HIV clinics. To optimize the tool for the Kenyan setting, we will invite stakeholder to an intervention development workshop. Existing services, the number of steps, as well as the system for assigning and re-assigning steps will be discussed.

The study team will develop job aids, training material and other identified tools to support intervention administration activities in the pilot phase and refine the material for the RCT phase. Intervention sites will be trained on how to deliver the intervention prior to implementation. As there will be varying skill and service delivery options across participating facilities, the study team

Adapted from NIH Behavioral and Social Intervention Clinical Trial Protocol Template v3.0 - 20180827

will work with HCWs to improve their ability to use the DiSC intervention during initial implementation period (about 3-6 months) during which an implementation/adaptation log will be used to track changes in implementation and HCWs will participate in twice-monthly planning and feedback meetings.

Surveys and tracking tools will be used to track implementation (see section 8).

6.3 MEASURES TO MINIMIZE BIAS: RANDOMIZATION AND BLINDING

Randomization procedures are described in section 4.1. Blinding is not possible as the intervention will be delivered at the clinic level.

6.4 STUDY INTERVENTION/EXPERIMENTAL MANIPULATION ADHERENCE

The study team will track ALHIV to determine if they received care as per assignment in the intervention sites using intervention adherence logs. These logs will be adapted based on the final intervention steps.

6.5 CONCOMITANT THERAPY

NA

6.5.1 RESCUE THERAPY

NA

7 STUDY INTERVENTION/EXPERIMENTAL MANIPULATION DISCONTINUATION AND PARTICIPANT DISCONTINUATION/WITHDRAWAL

7.1 DISCONTINUATION OF STUDY INTERVENTION/EXPERIMENTAL MANIPULATION

We do not anticipate that clinics will discontinue participation or withdraw from the study after randomization. However, if this occurs, the study team will get permission from the clinic to use study data up until the time of discontinuation.

7.2 PARTICIPANT DISCONTINUATION/WITHDRAWAL FROM THE STUDY

Participants are free to withdraw from participation in surveys or individual data collection procedures at any time upon request. Participants may also be discontinued if there is:

- Lost to Follow-up; unable to contact subject (see Section 7.3, Lost to Follow-Up)

Adapted from NIH Behavioral and Social Intervention Clinical Trial Protocol Template v3.0 - 20180827

- Any event or medical condition or situation occurs such that continued collection of follow-up study data would not be in the best interest of the participant
- The participant meets an exclusion criterion (either newly developed or not previously recognized) that precludes further study participation

The reason for participant discontinuation or withdrawal from the study will be recorded. Subjects who sign the informed consent form and withdraw or discontinue may be replaced.

